9.3.2. Unsolicited Adverse Events

The frequency of all unsolicited AEs reported per subject from first administration of study vaccine to 28 days after the last vaccination are presented by MedDRA SOC, PT, severity, relationship to study treatment, and baseline flavivirus status in [Table 129](#) (2.5 mcg ZPIV), [Table 130](#) (5 mcg ZPIV), and [Table 131](#) (placebo).

The frequency of all unsolicited AEs reported per subject from first administration of study vaccine to 28 days after the last vaccination are presented in the following tables by MedDRA SOC, PT, severity, dose, and baseline flavivirus status in [Table 132](#) (2.5 mcg ZPIV), [Table 133](#) (5 mcg ZPIV), and [Table 134](#) (placebo).

[Figure 58](#), [Figure 59](#), and [Figure 60](#) are graphical representations of the number and severity of all unsolicited adverse events overall and by treatment group and MedDRA SOC following any dose, post dose 1, and post dose 2, respectively. Similar presentations for adverse events determined to be related to study product are available in [Figure 61](#), [Figure 62](#), and [Figure 63](#).

Refer to [Listing 11](#) for a detailed listing of all unsolicited adverse events. [Table 189](#) includes a listing of all serious adverse events and [Table 190](#) includes a listing of all non-serious unsolicited moderate or severe adverse events.

9.4. Deaths, Serious Adverse Events and other Significant Adverse Events

Serious adverse events including deaths will be listed in [Table 189](#). A listing of AESIs and NOCMCs will be presented in [Table 191](#).

The number and percentage of subjects reporting new onset chronic medical conditions is summarized by MedDRA SOC and PT by treatment group and baseline flavivirus immune status in [Table 135](#).

Similar summaries for the number and percentage of subjects reporting AESIs related to study treatment are presented in [Table 136](#). The duration in days of AESIs is summarized in [Table 137](#).

Summaries of the number of subjects reporting serious adverse events related to study treatment are available in [Table 138](#). The duration in days of the related SAEs is summarized in [Table 139](#).

9.5. Pregnancies

For any subjects in the Safety population who became pregnant during the study, every attempt was made to follow these subjects to completion of pregnancy to document the outcome, including information regarding any complications with pregnancy and/or delivery. A listing of pregnancies and outcomes will be presented ([Listing 20](#), [Listing 24](#), [Listing 25](#), [Listing 26](#), and [Listing 27](#)).

9.6. Clinical Laboratory Evaluations

Safety laboratory tests include WBC, hemoglobin, hematocrit and platelets for hematology; ALT, AST, total bilirubin, BUN, and creatinine for chemistry; and urine dipstick for protein and glucose for urinalysis. [Table 192](#) (chemistry), [Table 193](#) (hematology) and [Table 194](#) (urinalysis) are listings of all abnormal laboratory results.

The severity of clinical lab results by frequency and proportion of subjects for chemistry, hematology, and urinalysis clinical laboratory parameters conducted at screening (baseline) and Days 8, 15, 36, 43, and by maximum severity post-baseline are presented overall and by pre-vaccination flavivirus immune status and parameter as listed in [Table B](#) below.

The frequency and proportion of subjects with abnormal hematology, chemistry and urinalysis clinical laboratory parameters related to study treatment at each timepoint and by maximum severity post-baseline are presented by pre-vaccination flavivirus immune status and parameter as listed in [Table C](#) below.

Descriptive statistics of each hematology and chemistry clinical laboratory parameter at each scheduled time point, including change from baseline statistics, are presented by parameter as listed in [Table D](#) below.

Labs may also be performed as necessary at unscheduled visits for follow-up of an adverse event.

[Figure 64](#), [Figure 65](#), and [Figure 66](#) display abnormal results by laboratory parameter, severity, and treatment group and includes all values reported after treatment administration (scheduled and supplemental) for chemistry, hematology, and urinalysis labs, respectively. Mean changes from baseline at each scheduled time point for each chemistry and hematology lab are presented by treatment group in [Figure 67](#) through [Figure 75](#). [Listing 17](#), [Listing 18](#), and [Listing 19](#) include listings of chemistry, hematology, and urinalysis results at any time post-treatment administration, respectively.

Table B: Severity of Clinical Lab Results:

Any Chemistry Parameter	Table 195
ALT	Table 196
AST	Table 197
Total Bilirubin	Table 198
BUN	Table 199
Creatinine	Table 200
Any Hematology Parameter	Table 212

WBC	Table 213
Hemoglobin	Table 214
Hematocrit	Table 215
Platelet Count	Table 216
Any Urinalysis Parameter	Table 226
Protein	Table 227
Glucose	Table 228

Table C: Severity of Abnormal Clinical Lab Results Related to Study Treatment

Any Chemistry Parameter	Table 201
ALT	Table 202
AST	Table 203
Total Bilirubin	Table 204
BUN	Table 205
Creatinine	Table 206
Any Hematology Parameter	Table 217
WBC	Table 218
Hemoglobin	Table 219
Hematocrit	Table 220
Platelet Count	Table 221
Any Urinalysis Parameter	Table 229
Protein	Table 230
Glucose	Table 231

Table D: Descriptive Statistics of Chemistry and Hematology Clinical Lab Results

	All Subjects
Chemistry Parameters	
ALT	Table 207
AST	Table 208
Total Bilirubin	Table 209
BUN	Table 210
Creatinine	Table 211
Hematology Parameters	

WBC	Table 222
Hemoglobin	Table 223
Hematocrit	Table 224
Platelet Count	Table 225

9.7. Vital Signs and Physical Evaluations

Vital sign measurements included systolic blood pressure, diastolic blood pressure, pulse, and oral temperature. The frequency and proportion of subjects with abnormal vital signs results is presented by study visit, treatment group and severity in [Table 232](#) (any assessment), [Table 233](#) (oral temperature), [Table 234](#) (pulse), [Table 235](#) (systolic blood pressure) and [Table 236](#) (diastolic blood pressure). [Listing 20](#) includes a listing of vital signs at any time post-treatment administration; physical exam findings are presented in [Listing 21](#).

9.8. Concomitant Medications

Concomitant medications will be summarized in [Table 237](#) by WHO ATC Code Levels 1 and 2 and by treatment group. A listing of concomitant medications is presented in [Listing 22](#).

9.9. Other Safety Measures

Summary tables of acute febrile illness (AFI) and acute rash illness (ARI) events will be presented. The percentage of subjects who develop ARI or AFI will be summarized by treatment group and baseline flavivirus status. Additionally, summary tables for AFI/ARI events will be presented by baseline flavivirus status.

Summaries of subjects reporting any events, any medically treated events, and any events requiring concomitant medication, including the total number of events and the number, percentage and exact 95% Clopper-Pearson CI of subjects reporting an event, will be presented for all subjects and by baseline flavivirus immune status in [Table 140](#), [Table 141](#), [Table 142](#), [Table 143](#), and [Table 144](#). Similar summaries presented by infection confirmation method are presented in [Table 147](#), [Table 148](#), [Table 149](#), [Table 150](#) and [Table 151](#).

Summaries of laboratory confirmed ZIKV and DENV infections are also presented. ZIKV and DENV infection is presented via two methods: subjects presenting with ARI/AFI and positive Arbovirus PCR result within 14 days of symptom onset or subjects presenting with ARI/AFI and a 4-fold rise in ZIKV or DENV titers following the onset of illness compared to prior to illness. The total number of laboratory confirmed ZIKV or DENV infections are summarized by treatment group, baseline flavivirus status, and confirmation method in [Table 154](#), [Table 155](#), [Table 156](#), [Table 157](#), and [Table 158](#).

The distribution of the maximum severity of symptoms of each ARI/AFI event by baseline flavivirus status and treatment group will be presented in [Table 161](#), [Table 162](#), [Table 163](#), [Table 164](#), and [Table 165](#), as well as by infection confirmation status in [Table 168](#), [Table 169](#), [Table 170](#), [Table 171](#), and [Table 172](#). For subjects reporting at least one AFI/ARI the duration of reported symptoms will be described in [Table 175](#), [Table 176](#), [Table 177](#), [Table 178](#), [Table 179](#), and by infection confirmation status in [Table 182](#), [Table 183](#), [Table 184](#), [Table 185](#), and [Table 186](#).

Individual subject listings of AFI/ARI data will be included in [Listing 12](#) (subject information), [Listing 13](#) (medical treatment sought for ARI/AI), [Listing 14](#) (ARI/AI symptoms), [Listing 15](#) (vital signs), and [Listing 16](#) (laboratory results).

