### **3.1.3 Exploratory**

1. Estimate the incidence of ZIKV and DENV infections between Visit 00 and the subject's last visit and describe the clinical presentation including disease severity overall, by dosage group, product received, and pre-vaccination flavivirus immune status.

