#### **11.4.4 Surveillance Analysis**

We will describe the number and proportion of subjects who develop an AFI or an ARI who have ZIKV or DENV RNA or other evidence of acute ZIKV or DENV infection detected within 14 days of symptom onset. We will analyze these endpoints for all subjects overall, and by treatment group and pre-vaccination flavivirus immune status. We will also describe the severity of these laboratory confirmed ZIKV and DENV infections overall, by treatment group, and pre-vaccination immune status. Severity endpoints for ZIKV infection severity will be defined using duration of symptoms, grade of symptoms, use of concomitant medications, and need for hospitalization or other medical care. Severity endpoints for DENV infections will be based on these items as outlined in the 1997 and 2009 World Health Organization (WHO) guidelines.

Please see the separate Statistical Analysis Plan for additional information.

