1. PREFACE

This Statistical Analysis Plan (SAP) for DMID Protocol 16-0034, “*Phase I, Randomized, Double-blinded, Placebo-Controlled Dose De-escalation Study to Evaluate the Safety and Immunogenicity of Alum Adjuvanted Zika Virus Purified Inactivated Vaccine (ZPIV) Administered by the Intramuscular Route in adult Subjects Who Reside in a Flavivirus Endemic Area*

” describes and expands upon the statistical information presented in the protocol.

This document describes all planned analyses and provides reasons and justifications for these analyses. It also includes sample tables, listings, and figures planned for the final analyses. Regarding the final analyses and Clinical Study Report (CSR), this SAP follows the International Conference on Harmonisation of Technical Requirements for Registration of Pharmaceuticals for Human Use (ICH) Guidelines, as indicated in Topic E3 (Structure and Content of Clinical Study Reports), and more generally is consistent with Topic E8 (General Considerations for Clinical Trials) and Topic E9 (Statistical Principles for Clinical Trials). The structure and content of the SAP provides sufficient detail to meet the requirements identified by the FDA and ICH, while all work planned and reported for this SAP will follow internationally accepted guidelines published by the American Statistical Association and the Royal Statistical Society for statistical practice.

This document contains four sections: (1) a review of the study design, (2) general statistical considerations, (3) comprehensive statistical analysis methods for immunogenicity and safety outcomes, and (4) shells of proposed tables and data listings and mock figures. Within the table, figure, and listing mock-ups (Appendices 1, 2, and 3), references to CSR sections are included. Any deviation from this SAP will be described and justified in protocol amendments and/or in the CSR, as appropriate. The reader of this SAP is encouraged to also review the study protocol for details on conduct of the study and the operational aspects of clinical assessments.

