1. Number and proportion of subjects who develop an acute febrile illness (AFI) or an acute rash illness (ARI) who have evidence of acute ZIKV or DENV infection detected within 14 days of symptom onset. This endpoint will be analyzed for all subjects overall, and by dosage group, product received, and pre-vaccination flavivirus immune status.
2. Number and severity of laboratory confirmed ZIKV and DENV infections during the study, overall, by treatment group, and pre-vaccination immune status, where severity is described by:
 - Duration of symptoms
 - Grade of symptoms (mild, moderate, severe)
 - Use of concomitant medications
 - Need for hospitalization or other medical care

Laboratory confirmation will be made by AFI or ARI with either: 1) evidence of acute ZIKV and DENV infection within 14 days of symptom onset or 2) a 4-fold rise in DENV or ZIKV neutralization titers between samples collected at the last visit prior to and at the first visit following the AFI/ARI, where available.

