Table 142: Summary of AFI/ARI Events Reported Through 12 Months Post Final Vaccination by Treatment Group – Baseline ZIKV Seronegative Subjects**Table 143: Summary of AFI/ARI Events Reported Through 12 Months Post Final Vaccination by Treatment Group – Baseline ZIKV Seropositive and DENV Seropositive Subjects****Table 144: Summary of AFI/ARI Events Reported Through 12 Months Post Final Vaccination by Treatment Group – Baseline ZIKV Seropositive and DENV Seronegative Subjects****Table 145: Summary of AFI/ARI Events Reported Through 12 Months Post Final Vaccination by Treatment Group – Baseline ZIKV Seronegative and DENV Seropositive Subjects**

Table 146: Summary of AFI/ARI Events Reported Through 12 Months Post Final Vaccination by Treatment Group – Baseline ZIKV Seronegative and DENV Seronegative Subjects

Table 147: Number of Laboratory Confirmed ZIKV or DENV Infections Overall and by Confirmation Method – All Subjects

[Implementation note: This table can include any subjects who did not have a baseline flavivirus status observed.]

Infection Confirmation Status	2.5 mcg ZPIV (N=X)				5 mcg ZPIV (N=X)				Placebo (N=X)				All Subjects (N=X)			
	Number of Events	Number of Subjects	% of Subjects	95% CI	Number of Events	Number of Subjects	% of Subjects	95% CI	Number of Events	Number of Subjects	% of Subjects	95% CI	Number of Events	Number of Subjects	% of Subjects	95% CI
Positive by PCR ^a	X	X	XX	X.X, X.X	X	X	XX	X.X, X.X	X	X	XX	X.X, X.X	X	X	XX	X.X, X.X
Positive by 4-Fold Titer Rise ^b																
Any Positive Confirmation ^{a,b}																
Negative Lab Confirmation																

N = Number of subjects in the Safety Population

% = percentage of subjects reporting at least one AFI/ARI event/total number of subjects in the Safety population in the group

95% CI is calculated using the Clopper-Pearson methodology for a binomial distribution.

This table includes subjects who only received dose 1.

^a PCR confirmation includes a positive PCR result for at least one of ZIKV (blood or urine) or DENV.^b 4-fold rise in either ZIKV or DENV neutralization titers after the ARI/AFI illness visit compared to before the illness visit.^c Includes hospitalization or other medical care

Tables with similar format:

Table 148: Number of Laboratory Confirmed ZIKV or DENV Infections Overall and by Confirmation Method – Baseline ZIKV Seropositive Subjects

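### The SAP's confirmed-infection tables count Zika and dengue as one category, so neither virus's cases or severity by arm appear in any summary

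*SAP*

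**What the plan says.** Protocol 3.1.3 sets the aim: "Estimate the incidence of ZIKV and DENV infections between Visit 00 and the" last visit of each subject, with a description of the clinical presentation and severity. SAP 3.1 repeats it. The second exploratory endpoint is "Number and severity of laboratory confirmed ZIKV and DENV infections during the study, overall, by treatment group, and pre-vaccination immune status" (SAP 3.2; Protocol 3.2.3 has the same text).

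Protocol 11.4.4 treats severity virus by virus. For Zika: "Severity endpoints for ZIKV infection severity will be defined using duration of symptoms, grade of symptoms, use of concomitant medications", plus need for hospitalization or other care. For dengue: "Severity endpoints for DENV infections will be based on these items as outlined in the 1997 and 2009 World Health Organization (WHO) guidelines". It then refers the reader to the SAP, whose Preface states: "This document describes all planned analyses and provides reasons and justifications for these analyses".

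SAP 9.9 says: "The total number of laboratory confirmed ZIKV or DENV infections are summarized by treatment group, baseline flavivirus status, and confirmation method". On severity it says: "The distribution of the maximum severity of symptoms of each ARI/AFI event by baseline flavivirus status and treatment group will be presented in" one set of tables, with a second set by infection confirmation status. The footnote to Table 147 defines the PCR row: "PCR confirmation includes a positive PCR result for at least one of ZIKV (blood or urine) or DENV". The titer-rise row is likewise met by a rise for either virus.

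Listing 12 in SAP Appendix 3 has separate ZIKV and DENV columns for PCR and for the 4-fold titer rise. Listings 13 and 14 hold care sought, symptoms, severity and duration.

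**The concern.** Zika is the infection the vaccine is meant to prevent; dengue is not. A combined positive row mixes an outcome the vaccine might reduce with one for which no such effect is claimed. Write Z and D for the numbers positive for each virus and B for the number positive for both. The pooled row reports only Z + D − B, and none of the three can be recovered from it. A reader of the summary tables could not say how many dengue or Zika cases occurred in an arm, or how severe either was. That is what the objective asks, and the baseline side of the same tables is already split by ZIKV and DENV serostatus.

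**Working it through.** No sample-size, power or alpha figure is involved, so the check is a reading and count of the shells.

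**Shells broken down by confirmation status (SAP Appendix 1).**

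| All Subjects shell | Content | Repeated as | Virus-specific rows |
|---|---|---|---|
| 147 | Number of confirmed infections | 148-153 | 0 |
| 154 | Events, by medication and medical treatment | 155-160 | 0 |
| 168 | Maximum symptom severity | 169-174 | 0 |
| 182 | Symptom duration | 183-188 | 0 |

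All four use the same rows: positive by PCR, positive by 4-fold titer rise, any positive, negative. The footnotes to 147, 154 and 182 define a positive as either virus. Table 168 does not print the PCR footnote, but its title and titer note both join the viruses with *or*. The tally is 4 designs × (1 + 6 strata) = 28 shells, with 0 showing either virus alone. SAP 9.9 names five from each set, 4 × 5 = 20.

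**Everything else on these illnesses.** Tables 140-146, 161-167 and 175-181 are not split by confirmation status: 7 + 7 + 7 = 21, and 28 + 21 = 49, which is all of Tables 140-188. The list of 75 figures has none on febrile or rash illness. The viruses are separated only in listings.

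**Text against shells.** SAP 9.9 assigns the count of confirmed infections to Tables 154-158, and the event summaries with medication and treatment to 147-151. The shell titles are the other way round.

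**Titer confirmation and vaccine response.** SAP 3.3 defines MN50 seroconversion as at least a 4-fold rise from baseline. It also accepts a 4-fold rise in ZIKV or DENV neutralization titer between the visits flanking an illness as confirmation. Humoral samples are drawn on Days 1, 15, 29, 43 and 57, then at four later visits, and the Day 1 and Day 29 samples are taken before the dose. An illness between Days 1 and 15, or 29 and 43, therefore has flanking samples on either side of a dose, and a missing sample widens the interval. In a ZPIV recipient such a ZIKV rise may be the response to vaccine. The pooled row already has this weakness, but a row named confirmed ZIKV would make it more misleading.

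**Size of the change.** Blocks to extend: 1 in Table 147, 3 in Table 154, and 18 each in Tables 168 and 182 (17 symptoms plus Any Symptom), so 1 + 3 + 18 + 18 = 40. Splitting only Any Symptom in the last two gives 1 + 3 + 1 + 1 = 6. One any-method row per virus costs 6 × 2 = 12 rows. PCR, titer and any-method rows for each virus cost 6 × 6 = 36.

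**The case against.** The strongest reply is that no list of groupings asks for a split by virus. Objective 1 names dosage group, product received and immune status; endpoint 2 names treatment group and immune status. The first exploratory endpoint and the opening of Protocol 11.4.4 join the viruses with *or*, which supports pooling in a count table. The case for splitting rests on the objective, which names both infections, and on two sentences in a section the protocol calls abbreviated. This stands. A reader might infer that the SAP breaches an explicit by-virus commitment; the documents do not support that.

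A reader might also take 28 pooled shells as 28 failings. They are four designs repeated over strata, so this is one choice.

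Nor should it be inferred that the SAP drops a defined dengue severity classification. Protocol 11.4.4 points to the same four items as outlined in the WHO guidelines and states no categories. The SAP tabulates lethargy, restlessness, respiratory distress, persistent vomiting and bleeding, but whether these match the guidelines cannot be judged here. Protocol 8.7 specifies only infection testing at illness visits, and 8.6 leaves other labs to the investigator, so a full classification may not be derivable. What remains is that the reference is neither applied nor retired, although SAP Section 15 records another change to this endpoint.

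Finally, the endpoint is descriptive in a Phase 1 trial of about 90 subjects, and the listings preserve the data. That limits the consequence. It does not turn a listing into an incidence or severity summary.

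**Conclusion.** The point holds as an inexpensive improvement to an exploratory analysis. None of the four confirmed-infection designs shows Zika or dengue alone, so the number and severity of each by arm must be compiled by hand from Listings 12-14. The conclusion rests on the Appendix 1 shells and SAP 9.9 being the full set of planned summaries, as the Preface says. With no attack rate in the documents, the number of cases could be zero or several; a zero for one virus would itself be informative. No safety or immunogenicity result, power figure or error rate is affected. The WHO dengue reference is secondary.

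**What to change.** In SAP 9.9 and the All Subjects Tables 147, 154, 168 and 182:

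1. Add confirmed-ZIKV and confirmed-DENV rows from the virus-specific fields in Listing 12, with PCR and titer-rise confirmation kept apart and an any-method row for each virus. In Tables 168 and 182, do this at least for the Any Symptom block. Keep the pooled rows.
2. Count an episode positive for both viruses in each virus's row, and footnote how many there are.
3. Flag any episode whose flanking samples straddle a ZPIV dose, and do not count it as confirmed ZIKV on titer alone.
4. Correct the swapped references to Tables 147-151 and 154-158.
5. Apply the WHO dengue guidelines if the collected data allow, or state in Section 15 that they are not used and why.

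The cost is SAP wording and, for the lean version, 36 rows across four existing tables (12 with any-method rows only, which would not keep PCR and titer apart). No new data are needed. Many rows will be sparse. The two-subject rule in SAP 6.4 does not suppress All Subjects tables, and the stratum tables can stay as they are.
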